9.7 QMG responder rate (≥ 3.0 points improvement from Baseline)

Participants will be classified as QMG total score responders at a scheduled visit if the QMG total score is at least a 3-point improvement (decrease) from Baseline.

The number and percentage of observed QMG responders at each scheduled post-Baseline visit will be summarized by study cycle, actual dose level received within study cycle, and RLZ total using descriptive statistics.

Additional summary of observed QMG responders by fixed dose and weight subgroups will also be conducted as specified in [Section 4.9.2](#).

9.8 MG-C responder rate (≥ 3.0 points improvement from Baseline)

Participants will be classified as MG-C total score responders at a scheduled visit if the MG-C total score is at least a 3-point improvement (decrease) from Baseline.

The number and percentage of observed MG-C responders at each scheduled post-Baseline visit will be summarized by study cycle, actual dose level received within study cycle, and RLZ total using descriptive statistics.

Additional summary of observed MG-C responders by fixed dose and weight subgroups will also be conducted as specified in [Section 4.9.2](#).

9.9 EQ-5D-5L

The EQ-5D-5L essentially consists of 2 pages: the EQ-5D descriptive system and the EQ visual analogue scale (EQ VAS).

A frequency table will be produced to summarize answers provided to each of the 5 dimensions of the EQ-5D descriptive system at each scheduled visit by study cycle, actual dose level received within study cycle, and RLZ total.

The observed value of EQ VAS and change from Baseline will be summarized by study cycle, actual dose level received within study cycle, and RLZ total using descriptive statistics. No imputation will be applied on missing item in EQ-5D descriptive system and EQ VAS.

A by-participant listings of EQ-5D-5L will be provided.

9.10 MG-QOL15r

The MG-QOL15r total score is calculated by adding all the individual items described in [Section 13.5](#).

The MG-QOL15r total score and change from Baseline to Day 43 will be summarized by study cycle, actual dose level received within study cycle, and RLZ total.

The mean change from Baseline in MG-QOL15r over time will be plotted by study cycle and treatment group.

A by-participant listings of MG-QOL15r will be provided.

9.11 Time between consecutive treatment cycles

The time between treatment cycles is calculated as: date of first sc infusion in consecutive cycle - date of last sc infusion before new cycle + 1 (or date of censoring - date of last sc infusion before potential new cycle + 1).

Discontinued participants will be censored at their discontinuation date and completers will be censored at their last visit date.

The number and percentage of study participants with ≤ 21 , $21 <= 28$, $28 <= 60$, $60 <= 90$, $90 <= 120$, $120 <= 150$, $150 <= 180$, $180 <= 300$, $300 <= 400$, $400 <= 500$, ..., $900 <= 1000$ days between study cycles will be summarized by treatment group in the proceeding cycle and RLZ total. Mean, SD, median, min and max will also be calculated for time between consecutive treatment cycles by treatment groups in the proceeding cycle and RLZ total. The same summaries will be repeated but participants who had no event in a specific cycle will be excluded from that cycle analysis.

Survival estimates for day 1, 28, 60, 90, 120, 150, 180, 300, 400, 500, 600, 700, 800, 900 and 1000 will be calculated using Kaplan-Meier method by treatment group in proceeding cycle and

RLZ total. The median times (with 95% CI) between study cycles and cumulative number of events by study cycle will also be reported. The survival event is defined as the start of subsequent cycle since last sc infusion of preceding cycle. Number of censored participants will be reported as well.

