4.4 End of study definition

A study participant is considered to have completed the study if he/she has completed all phases of the study including the first 8 weeks of the Observation Period and the EOS visit assessments.

At the time of product approval or the availability of a MAP, or study participant early withdrawal the following scenarios need to be considered:

- if the study participant is still in a treatment cycle, he/she will need to complete that cycle and the first 8 weeks of the Observation Period before completing the EOS visit assessments.
- if a study participant is in the first 8 weeks of the Observation Period in, he/she must complete the 8 weeks before completing the EOS visit assessments
- if a study participant is in the beyond the first 8 weeks of the Observation Period or in the no treatment period, he/she can complete EOS visit assessments

The end of the study is defined as the date of the last visit of the last participant in the study.

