Those patients who received rescue therapy (IVIg, PEX, SCIg, or iv corticosteroid) during the observation or no treatment with rozanolixizumab periods may continue in the study at the Investigator's discretion and after discussion with Medical Monitor and/or UCB Study Physician. The following cycle of rozanolixizumab should in general not start earlier than 4 weeks following the last dose of IVIg, SCIg, or iv corticosteroids or the last PEX session, unless there is a medical reason, and an earlier treatment initiation is being considered [REDACTED] for the study participant as agreed upon with the Medical Monitor and/or UCB Study physician.

Study participants (not withdrawn from the study) will continue in the study and until product approval or until transition to a managed access program (MAP), if available, as indicated per the Sponsor, and according to local guidance.

Figure 2–2: MG0007 study schema

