5.1 Subject disposition

The following outputs will be created.

Summaries:

- **Reasons for screen failures** (as collected on the Study Termination Screen Failure CRF page) will be tabulated using the ES for overall. Additionally, the reasons for screen failures will be summarized by during and post- the COVID-19 pandemic based on the screen failure date relative to the pandemic cut-off date.
- **Disposition of study participants screened** will be tabulated using the ES for overall, by region and by site. In this summary, the site number, principal investigator name, first participant in date and last participant out date, will be captured by first actual treatment and by each analysis set (FAS and SS).
- **Disposition of analysis sets** will be summarized by the first cycle treatment group, RLZ total, total and analysis sets (ES, FAS and SS) using the ES.
- **Disposition and discontinuation reasons** will be tabulated using the FAS and SS, and will contain the number and percentage of study participants by treatment group, overall and by during and post- the COVID-19 pandemic who:
 - Started Study
 - Completed Study
 - Discontinued Study with primary reason for discontinuation (primary reason for premature study termination as collected in the Study Termination Enrolled CRF)

Note: The summary by during and post- the COVID-19 pandemic will be based on the start, completed and discontinuation date relative to the pandemic cut-off date which will be presented in the same table. The discontinuation reason in each period will also be summarized. Discontinuation due to COVID-19 pandemic as well as discontinuation due to transition to MG0020 study will be summarized as sub-category under “Other” reason.

- **Discontinuation due to AEs** will be presented using the FAS and SS to display the total number of study participants who discontinued the study due to AEs by treatment group, RLZ total, total and the categories: AE serious fatal, AE non-fatal and other (AE non-serious fatal).
- **Count of participant by visit** using SS will summarize the number of participants at each visit by treatment group.

- **Impact of COVID-19** will be presented using the FAS to display the number and percentage of participants in each impact category by treatment group, RLZ total, total and visit.

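### SAP 9.11 summarizes censored gaps as if they were finished, so the plain table of time between cycles runs short; Kaplan-Meier should be named as the main presentation

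*SAP*

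**What the plan says.** SAP 9.11 defines one duration. When a new cycle starts, it runs from the last infusion of the previous cycle to the first infusion of the next. When none starts, the same variable takes the censored duration ("or date of censoring - date of last sc infusion before potential new cycle + 1"). The censoring dates are given: "Discontinued participants will be censored at their discontinuation date and completers will be censored at their last visit date".

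Three presentations follow:

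- **Plain summary.** Counts and percentages by day range, and "Mean, SD, median, min and max will also be calculated for time between consecutive treatment cycles".
- **Plain summary without open gaps.** "The same summaries will be repeated but participants who had no event in a specific cycle will be excluded from that cycle analysis".
- **Kaplan-Meier.** Estimates at fixed days, the median with 95% CI, cumulative events, and "Number of censored participants will be reported as well".

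Neither SAP 9.11 nor protocol 9.4.1 says which of these is the result. Protocol 9.4.1 reads the endpoint as information on how long the drug's effect lasts.

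**The concern.** The sentence that repeats the summaries without no-event participants shows that the first table includes them. A participant who leaves 70 days into a gap with no new cycle is recorded as having had a 70-day gap. That value is only a lower bound.

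Exits in mid-gap are built into the design. Participants continue "until product approval or until transition to a managed access program (MAP), if available" (SAP 2.3.1). Under SAP 5.1, "discontinuation due to transition to MG0020 study will be summarized as sub-category" of the discontinuation reasons. Protocol Appendix 8 limits participation in Denmark and the UK to 14 months. Under protocol 4.4, anyone beyond the first 8 weeks of observation may go straight to the end-of-study visit.

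When follow-up ends at an administrative date, later cycles have less time left and are censored more often. The plain figures then tend to fall with cycle number even if the true gap is constant. The study is meant to show how long participants go before the next treatment over successive cycles, so a false decline would bear directly on that question. Nothing is tested; the harm is a wrong reported figure beside a Kaplan-Meier table that disagrees with it.

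**Working it through.** **1. Figure to reproduce.** There is none. The documents state no gap length, censoring share or event count for this endpoint.

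**2. Direction.** Let T be the true gap and C the time to censoring. The plain variable is min(T, C), which never exceeds T provided a new cycle can start at any time up to censoring. Its mean and median cannot exceed those of T, and shares of long gaps are understated.

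**3. An example that can be checked by hand.** Assume T = 28 + exponential with mean m (28 days is the 4-week minimum in protocol 4.1) and a true median of 120 days. Assume C = 56 + exponential with mean c, independent of T (56 days is the 8 weeks of protocol 4.4), with 25% of gaps censored.

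- m = (120 − 28)/ln 2 = 132.7; true mean 28 + 132.7 = 160.7.
- q = exp(−28/m) = 0.810. The share censored is q·m/(m + c) = 0.25, so c = 297.2. Let h = m·c/(m + c) = 91.75.
- Plain mean = 28 + m(1 − q) + q·h = 28 + 25.2 + 74.3 = 127.5, against 160.7.
- Plain median = 56 + h·ln(q/0.5) = 56 + 44.2 = 100.2, against 120.
- Share over 180 days: plain q·exp(−124/h) = 21.0%; true exp(−152/m) = 31.8%.
- Mean of completed gaps only = [127.5 − 0.25 × (56 + 91.75)]/0.75 = 120.8, lower still.
- Kaplan-Meier recovers the median of 120, because censoring is independent.

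**4. By cycle.** Simulation of 400,000 participants with the same gap distribution in every cycle: 28 + exponential with mean 70 (true mean 98, median 28 + 70·ln 2 = 76.5) or mean 150 (true mean 178, median 132.0). Each cycle has six weekly infusions (35 days from first to last). The administrative end is uniform on 360–1080 days, which is assumed. A cycle under way is completed, no new cycle starts after the administrative end (the documents do not say), and open gaps are censored at the later of that date and last infusion + 56 days.

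| After cycle | 1 | 2 | 3 | 4 |
|---|---|---|---|---|
| **True mean 98:** censored, % | 0 | 2 | 7 | 16 |
| plain mean | 98 | 97 | 93 | 89 |
| plain median | 76 | 76 | 73 | 68 |
| completed-gaps mean | 98 | 96 | 92 | 89 |
| share over 90 days, % (true 41) | 41 | 41 | 39 | 35 |
| Kaplan-Meier median | 76 | 77 | 77 | 79 |
| **True mean 178:** censored, % | 3 | 13 | 27 | 39 |
| plain mean | 173 | 159 | 140 | 124 |
| plain median | 132 | 124 | 106 | 90 |
| completed-gaps mean | 165 | 151 | 137 | 126 |
| share over 180 days, % (true 36) | 36 | 33 | 27 | 21 |
| Kaplan-Meier median | 132 | 133 | 135 | 137 |

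**5. Other exit patterns.**

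- *14 months for everyone* (applies only to Denmark and the UK): plain means 98/94/80/64 and 165/128/89/65.
- *Constant exit rate, mean 24 months:* no fall with cycle, but low throughout: 89 against 98, and about 145 against 178.
- *Participants differ* (individual exponential means multiplied by a lognormal factor, SD 0.8 on the log scale; 12–36 months): participants with short gaps dominate later cycles, so the true mean among those reaching each cycle falls, and the plain mean falls further. True 98/96/92/86 against plain 96/90/82/75; true 178/166/147/130 against plain 159/135/113/97. Kaplan-Meier medians fall too: 61/61/60/59 and 99/95/89/84.

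**The case against.** The strongest reply is that the correct analysis is already there. SAP 9.11 plans Kaplan-Meier estimates, the median with its interval, cumulative events and the number censored, and every efficacy analysis is descriptive. That is true. It limits the defect to presentation, but it does not make the first table right or tell the reader which table to believe.

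A second reply is that deleting one short table while keeping another is inconsistent. In the 178-day case the completed-gaps mean is lower than the plain mean after cycles 1 to 3 (165/151/137 against 173/159/140). Bias alone therefore does not separate the two. What does is that completed gaps are a defined quantity that can be labelled honestly, whereas a mixture of finished and open gaps describes nothing in particular. Labelling the first table as observed follow-up would be a milder alternative.

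Third, Kaplan-Meier is not free of drift. If no cycle can start in the closing 8 weeks (protocol 4.4: "he/she must complete the 8 weeks before completing the EOS visit assessments"), participants count as at risk when they are not, and the median rises. With 14 months of follow-up it reaches 89 against a true 76.5, or roughly 150 against 132, after cycle 4. With 12 to 36 months the rise is small (79 and 137), and it disappears if cycles may start in those weeks.

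Fourth, the size is unknown. With a true mean of 98 days and 12 to 36 months of follow-up, the bias after the first two cycles is negligible. The time bands in SAP 8.1 are reporting categories, not planned follow-up. All this stands: the direction is certain, the amount is not.

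**Conclusion.** The concern holds. As written, SAP 9.11 treats open gaps as finished, and its first plain summary is biased short for a secondary endpoint. Under the stated assumptions the plain mean after cycle 4 is about 9% low when the true mean is 98 days (89/98 = 0.91) and about 30% low when it is 178 days (124/178 = 0.70). The bias is small where few gaps are censored. A false decline over cycles appears when follow-up ends administratively; with a constant exit rate the figures are low but flat. These sizes depend on assumed gap distributions and exit patterns. The direction follows from the definition of the variable. Kaplan-Meier handles independent censoring but not the over-representation of short-gap participants in later cycles, which the SAP does not mention. The point should be corrected, but it affects reported figures and not any test.

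**What to change.** In SAP 9.11:

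1. Name Kaplan-Meier by cycle as the main presentation: median, quartiles, estimates at the planned days and number censored.
2. Delete the mean, SD, median, minimum, maximum and day-range percentages computed on censored times.
3. Keep the table without open gaps, label it 'completed gaps only', and put the already planned number censored beside it.
4. Add a footnote that later cycles over-represent participants with short gaps, so a fall in the Kaplan-Meier estimates by cycle is not by itself evidence that the effect is shortening.

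While the section is open, give a censoring date for participants still ongoing at a data cut. SAP 9.11 covers only discontinued participants and completers, and SAP 4.4 plans interim cuts.

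The cost is SAP wording and one deleted block of table rows, with no new data. Simple means would no longer be available to compare with earlier outputs, and Kaplan-Meier quartiles may not be reached in heavily censored late cycles.

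An optional addition, not a correction, is one Kaplan-Meier analysis with the event defined as next cycle or first rescue, whichever is earlier. Time to next cycle alone can overstate duration of effect when rescue is given in the gap. For a true median of 76.5 days, if rescue delays the next cycle by 28 days, the median becomes 78.2, 79.9 or 83.1 days at assumed rescue rates of 5, 10 or 20%.

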6.5.4 Rescue medication

The study site will supply rescue therapy that will be obtained locally. Rescue therapy will be given as per standard of care and at the discretion of the Investigator. Study participants who continue to experience moderate to severe symptoms despite treatment with rozanolixizumab may be treated with the following as rescue therapy:

- IVIg
- SC Ig
- PEX, or plasmapheresis
- iv corticosteroids at a higher dose than previous oral dose

Participants who are treated with rescue therapy during the Treatment Period are not eligible to receive any further treatment with rozanolixizumab. Study participants must complete the first 8 weeks of the Observation Period after the last dose of rozanolixizumab prior to completing the EOS visit assessments, and subsequently will be withdrawn from the study (Section 4.4).

Those patients who received rescue therapy during the observation or no treatment with rozanolixizumab periods may continue in the study at the Investigator's discretion and after discussion with Medical Monitor and/or UCB Study Physician. The following cycle of rozanolixizumab should in general not start earlier than 4 weeks following the last dose of IVIg, SC Ig, or iv corticosteroids or the last PEX session, unless there is a medical reason, and an earlier treatment initiation is being considered █ for the study participant as agreed upon with the Medical Monitor and/or UCB Study physician.

The date and time of rescue medication administration as well as the name and dosage regimen of the rescue medication must be recorded.

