9.2.1 Intercurrent event handling rationale and impact on the study

In MG0007, every study participant, except those coming from MG0004, will start with an initial fixed mandatory cycle. Prior to dosing in the initial fixed treatment cycle, the study participant will be assessed for MG worsening (eg, an increase of 2.0 points on the MG-ADL or 3.0 points on the QMG scale). The study participant will be initially randomized to rozanolixizumab equivalent to approximately 7mg/kg or 10mg/kg weekly (QW). After the first treatment cycle, dose adjustments may be applied at the start of each treatment cycle based on Investigator's discretion. Dose adjustments may not be applied during a treatment cycle.

For the assessment of safety and tolerability, adverse events (AEs) recorded up to 8 weeks after the last sc infusion will be utilized for main analyses, regardless of study participants receiving treatment with rescue therapy.

For the analyses of efficacy endpoints, the intercurrent events to be considered are the use of rescue therapy prior to Day 43 and permanent treatment discontinuation (or withdrawal from study) due to TEAEs. Efficacy endpoints will be summarized in line with a treatment policy approach. With this approach, rozanolixizumab results will be analyzed regardless of study participants receiving treatment with rescue therapy. Summaries will also be presented for the efficacy endpoints where participants will be censored at the time that they take rescue medication.

Missing values will not be imputed.

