9.4 Planned efficacy and other analyses

9.4.1 Efficacy analyses

The main efficacy endpoint is the "Change from Baseline (Day 1) to Day 43 in MG-ADL score," for each of the first three 6-week treatment cycles where the Baseline of the respective cycle will be used as reference.

The summaries will be provided overall and by randomized treatment in-line with a treatment policy approach. Observed results will be presented for the different cycles (1 to n) regardless of the first cycle being mandatory or not. Missing values will not be imputed. Further summaries will be presented by the treatment received in each cycle.

The other secondary efficacy endpoints, Change from Baseline (Day 1) to Day 43 in QMG score, Change from Baseline (Day 1) to Day 43 in MG-C score, Change from Baseline (Day 1) to Day 43 in MG Symptoms PRO 'Muscle Weakness Fatigability' score, Change from Baseline (Day 1) to Day 43 in MG Symptoms PRO 'Physical Fatigue' score, and Change from Baseline (Day 1) to Day 43 in MG Symptoms PRO 'Bulbar symptoms' score, will be analyzed in the same way as the main secondary endpoint based on the MG-ADL.

Time to MG-ADL response (≥ 2.0 -point improvement from Baseline [Day 1]) for each treatment cycle will be summarized using time-to-event methodology (Kaplan Meier).

The time between consecutive treatment cycles will be summarized in order to provide information on how long the effect of rozanolixizumab lasts, ie, how long it will take to introduce a new cycle.

The number and percentage of participants achieving Minimal Symptom Expression (MG-ADL score of 0 or 1) at any time during the Treatment and Observation Periods will be summarized by cycle and by dose administration in that cycle.

Additionally, the number of treatment cycles will be summarized by treatment group.

Further summaries will be described in the SAP.

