3.9 Changes to protocol-defined analyses

In the protocol section 9.2.1, the intercurrent events to be considered are the use of rescue therapy prior to Day 43 and permanent treatment discontinuation (or withdrawal from study) due to TEAEs. In the SAP, we consider use of rescue therapy prior to Day 43 and permanent treatment discontinuation due to TEAEs as intercurrent events.

In the protocol, the treatment policy strategy is described for the analysis meaning that all data was planned to be analyzed regardless of study participants receiving treatment with rescue therapy. Summaries will also be presented for the efficacy endpoints where participants will be censored at the time that they take rescue medication. In the SAP, time to MG-ADL response will be analyzed censoring the data at the time of the use of rescue therapy and all other efficacy endpoints will be summarized following treatment policy.

Protocol amendment 3 did not mention how to treat IgG when participants receive rescue therapy. In the SAP, the IgG values up to and including 8 weeks after start date of rescue therapy will be excluded from the analysis.

In the protocol section 8.3.1, Hy's law is defined as $>3 \times \text{ULN}$ ALT or AST with coexisting $>2 \times \text{ULN}$ total bilirubin in the absence of $<2 \times \text{ULN}$ ALP, with no alternative explanation for the biochemical abnormality (ie, without waiting for any additional etiologic investigations to have been concluded). In this SAP, Hy's law is defined as (AST or ALT $\geq 3 \times \text{ULN}$) and TBL $\geq 2 \times \text{ULN}$ and ALP $< 2 \times \text{ULN}$ to be consistent with Rozanolixizumab program SAP.

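### Time between cycles (SAP 9.11) takes no account of rescue therapy, so it leans towards a longer apparent duration of effect, by an amount that depends on an unstated rescue rate

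*SAP*

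**What the plan says.** Protocol 9.4.1 says that the time between consecutive cycles is summarized "in order to provide information on how long the effect of rozanolixizumab lasts, ie, how long it will take to introduce a new cycle". It is a secondary efficacy endpoint.

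SAP 9.11 runs the interval from the last infusion of one cycle to the first infusion of the next, counting both days. The event is defined in one sentence: "The survival event is defined as the start of subsequent cycle since last sc infusion of preceding cycle". So is the censoring: "Discontinued participants will be censored at their discontinuation date and completers will be censored at their last visit date". One set of descriptive summaries uses the censored times as durations. A repeat set leaves out participants without an event in that cycle. Rescue is not mentioned.

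Protocol 6.5.4 treats rescue in two ways:

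- **Between cycles.** The participant may continue at the Investigator's discretion after discussion with the sponsor's physicians. The next cycle "should in general not start earlier than 4 weeks following the last dose of IVIg" (or of the other rescue therapies), with an exception for a medical reason.
- **During treatment.** "Participants who are treated with rescue therapy during the Treatment Period are not eligible to receive any further treatment with rozanolixizumab". These participants complete 8 weeks after the last dose and are then withdrawn.

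Protocol 9.2.1 adopts treatment policy for efficacy and adds: "Summaries will also be presented for the efficacy endpoints where participants will be censored at the time that they take rescue medication". SAP 3.9 keeps rescue censoring for time to MG-ADL response and states that "all other efficacy endpoints will be summarized following treatment policy".

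**The concern.** The interval to the next cycle tracks loss of effect well only if a new cycle is the usual response when the effect wears off. Protocol 6.5.4 provides a second response, rescue, and that response delays the next cycle or rules it out. A participant whose symptoms return and who receives IVIg or PEX is then recorded as still waiting for the event, although the benefit of the preceding cycle has ended.

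Both routes push the same way. Rescue between cycles lengthens the interval or turns it into a censored one. Rescue during treatment removes the event altogether. A dose group or cycle with more rescue could therefore look longer-lasting in this table than it was.

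**Working it through.** The documents state no expected gap, rescue rate or power for this endpoint, so there is no planned figure to reproduce. The check has three steps.

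**Step 1: dates, from the documents' own rules.** SAP 9.11 computes gap = date of next first infusion − date of last infusion + 1. Let rescue start on day x after the last infusion.

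- Time to rescue on the same scale: x + 1.
- Earliest recorded gap when the 4-week wait applies: x + 28 + 1 = x + 29. The wait runs from the last rescue dose or session, so a rescue course lasting several days adds its own length.
- Examples: x = 30 gives 31 against at least 59; x = 45 gives 46 against at least 74; x = 60 gives 61 against at least 89.
- Rescue during treatment, with the 8 weeks completed: event-free to at least 56 + 1 = 57 days, then censored.

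**Step 2: a simple illustration of rescue between cycles only.** Assume that need returns at 28 days plus an exponential time with mean 60 days, and that a share q of gaps gains exactly 28 days. Above day 56 the survival function is exp(−(t − 28)/60) × [1 − q + q·exp(28/60)], with exp(28/60) = 1.595. The median is therefore 28 + 60·ln 2 + 60·ln(1 + 0.595q).

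- q = 0: 69.6 days
- q = 5%: 71.4 days (+1.8)
- q = 10%: 73.1 days (+3.5)
- q = 20%: 76.3 days (+6.7)

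**Step 3: a simulation with both kinds of rescue.** There were 400,000 gaps per scenario. Assumptions:

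- Time to loss of effect is lognormal (log-SD 0.6), floored at day 29, with median 45, 60 or 90 days.
- Rescue occurs in 2 to 20% of gaps, half during treatment and half between cycles.
- After rescue between cycles, the next cycle starts 28 to 84 days later.
- Administrative censoring is uniform from day 60 to day 900.

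Each cell gives the Kaplan-Meier median in days under SAP 9.11, the median with rescue as an event, and the difference.

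| Rescue share | True median 45 | True median 60 | True median 90 |
|---|---|---|---|
| 2% | 45.7 / 44.6 / 1.1 | 60.8 / 59.5 / 1.3 | 90.9 / 89.4 / 1.5 |
| 5% | 46.9 / 44.2 / 2.7 | 62.2 / 58.9 / 3.3 | 92.0 / 88.3 / 3.7 |
| 10% | 48.9 / 43.2 / 5.7 | 64.4 / 57.7 / 6.7 | 93.9 / 86.4 / 7.5 |
| 20% | 54.7 / 41.5 / 13.2 | 69.2 / 55.2 / 14.0 | 98.3 / 82.5 / 15.8 |

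The proportion event-free at day 60 is overstated by 0.012 to 0.016 at 2% rescue, 0.031 to 0.040 at 5%, 0.061 to 0.079 at 10% and 0.121 to 0.160 at 20%.

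The simulation placed rescue during treatment at day 1. No other event or censoring occurs before day 29, so using the actual rescue start date, if that is before day 29, changes none of these figures.

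**The case against.** The strongest reply is that SAP 9.11 analyses the endpoint the protocol names. Protocol 9.4.1 itself equates duration of effect with the time to a new cycle, so a reader who infers that the event is simply an SAP error goes too far. SAP 9.11 implements the named endpoint; the weakness lies in reading the result as duration of effect without qualification.

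Other stronger readings also fail:

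- **That this is the study's only evidence on duration.** MG-ADL, QMG and MG-C changes and responder status are summarized at scheduled visits through the Observation Period (SAP 2.2.2.2), which protocol 2.1 says was chosen to study maintenance of effect.
- **That participants rescued during treatment are counted as long-lasting successes.** In the Kaplan-Meier analysis they are right-censored at about 8 weeks. The fault is informative censoring. In the descriptive summaries their censored times enter as durations in one set and are dropped from the other, so neither set shows a failure.
- **That every gap with rescue grows by 28 days.** The wait is a general rule with a medical exception.
- **That rescue is hidden.** Treatment policy is disclosed in SAP 3.9, and rescue use and time to rescue are reported by cycle and dose (SAP 11.2 and 11.3).
- **That protocol 9.2.1 plainly required rescue censoring here.** Its sentence covers the efficacy endpoints, but the intercurrent event it lists is rescue before Day 43, so its reach to later rescue is arguable.

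All analyses are descriptive and no decision rule depends on this one.

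What remains is that the separate rescue tables do not repair the interval. The main time-to-rescue analysis starts at the first dose in the study, not at the last infusion of a cycle, and neither output is combined with the gap.

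**Conclusion.** The concern holds in a limited form. Under SAP 9.11 as written, rescue can only lengthen or censor the interval, so the reported time overstates duration of effect to some degree. The date rules establish the direction; the size rests on assumptions, because the documents give neither a rescue rate nor a gap distribution.

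Across the two illustrations, the overstatement of the median is about 1 to 4 days at 2 to 5% rescue and 3 to 8 days at 10%. It reaches 13 to 16 days only in the 20% scenarios that include rescue during treatment. At low rates it is small. Unequal rescue between doses or cycles would distort those comparisons as well.

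A supplementary analysis and a clearer label are warranted. The documents do not support discarding the protocol-named endpoint.

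**What to change.** 1. Keep the present SAP 9.11 analysis and label it time to re-treatment.
2. Add a supplementary Kaplan-Meier analysis to SAP 9.11. The event is the earlier of the first infusion of the next cycle and the start of rescue therapy on or after the last infusion of the cycle. Rescue during the Treatment Period counts at its own start date and is not moved back to the last infusion.
3. Report the number of gaps containing rescue, by dose and cycle.
4. Either present the rescue-censored summary described in protocol 9.2.1 for this endpoint, or give the reason for dropping it in SAP 3.9. If it is presented, note that censoring at rescue is itself informative, so it does not replace item 2.

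The cost is SAP wording and one extra table, plus the rescue-censored summary if that option is taken. Rescue dates are already collected (protocol 6.5.4; SAP 6.4). The supplementary duration will be slightly shorter than the current one. No clinical rule changes.
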